### 7.0 Multisite -N/A

# **8.0** Study Timelines

- Phase 1: The total duration of an individual's participation in the study is no more than 1.5 hours. The number of study visits is 1 per participant. No follow-up is included in the study. It is anticipated that it will take approximately 10 minutes to consent each participant. The estimated date of completion for this phase of the study (focus group phase) and primary analyses is March 30, 2022.
- Phase 2: The total composite time duration of an individual's participation in the study is estimated to be about 60 minutes. The number of study visits is 3 per participant. All study "visits" are in the form of online survey and video viewing. The first study visit will consist of consenting via cover letter and pre-test. The second study visit will consist of a 1 month-follow-up survey video podcast viewing. The third study visit will consist of a short follow-up survey 3 months following post-test completion. It is anticipated that it will

take approximately 5 minutes to recruit/enroll each participant; 15 minutes to complete the pre-test; 20 minutes to watch draft podcast video; 15 minutes to complete the posttest; and 5 minutes to complete the 3-month follow-up. The estimated date of completion for this phase of the study and primary analyses is August 30, 2023.

# 9.0 Study Endpoints

- 9.1 The primary study endpoint for the proposed study shall be 3 months following the last participant's post-test in Phase 2 and been analyzed.
- 9.2 There are no primary or secondary safety endpoints to be described.
- 9.3 "There are no safety endpoints given that there are no safety risks associated with the study."

### 10.0 Procedures Involved

### 10.1 Study Design:

Phase 1: The study design is focus group methodology, a qualitative research design in which participants are guided through a freeform discussion of a particular issue. The results of will reflect perceptions about HIV that are validated directly from the participants themselves. Five focus groups will be conducted.

Phase 2: The study design is quantitative repeated measures methodology. Participant data will be de-identified and used aggregately in repeated measures analyses (N=128).

10.2 Phase 1: Participants will be introduced to the study and given written informed consent, with an opportunity to ask any study related questions. Participants will be notified that they will be digitally audio recorded throughout the duration of the focus group session. The moderator will introduce herself and instruct the participants to identify themselves with a pseudonym of their choice, and not to use their real names. The moderator will begin by asking the first question. Once discussion has begun, the moderator will guide the focus group discussion with a series of questions using the focus group script. [The focus group script of questions can be found in the SmartForms. The moderator will take notes throughout the focus group sessions that will provide context, if needed, throughout the discussion. The moderator will carefully watch the time, making sure that all questions are asked during discussion within the 1.5-hour time allotted for participation. Participants will be thanked for their participation, provided light refreshments, and will be given a Target, Amazon, or Wal-mart gift card of \$45 for participation.

Phase 2: Participants will email or call a dedicated study email/phone line, where research assistants will screen them, answer any questions they may have, and get them formally enrolled, if applicable. Participants will be given a unique ID number. Participants will be emailed a secure unique link to the pre-test survey (which will include cover letter consent information – See Section 22.1). Participants will complete the pre-test measure. One month after pre-test survey completion, participants will be emailed a secure unique line to the post-test survey in which they will view the podcast video and complete the post-test measures. Participants will be emailed a secure unique link 3 months later to complete a brief behavioral outcome questionnaire. The research team will be knowledgeable about the podcasting software in order to assist participants in trouble-shooting, if necessary. Dark Light Studios will also provide consulting throughout the entire research process, if needed. Upon pre-test completion, participants will be emailed (or pick up in person) a \$20 Walmart, Target, or Amazon gift card; \$80 Walmart, Target, or Amazon gift card upon post-test completion; and \$25 Walmart, Target, or Amazon gift card upon 3 month follow-up completion; for an opportunity to receive \$125 for complete participation. For participants who do not have email addresses, research assistants will assist them in obtaining one, within the recruitment procedures, if desired; alternately, participants will be able to schedule a time to meet at one of the community centers in order to complete pre- and post-test surveys in person, and/or to pick up gift card, if needed.

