# 1.0 Objectives

1.1 Aim 1 (Phase 1): To conduct 5 focus groups for the development of two theory-based, video podcast-delivered, HIV prevention interventions for self-identified heterosexual African American males and females. Aim 2 (Phase 2): To evaluate the effectiveness of the two theory-based, video podcast-delivered, HIV prevention interventions for self-identified heterosexual African American males and females.

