# 5.0 Number of Subjects

#### **LOCAL:**

- 5.1 Phase 1: Total number of subjects to be accrued locally = 35; Phase 2: Total number of subjects to be accrued locally = 128
- 5.2 NA The participant procedures involve no more than minimal risk.
- 5.3 Phase 1: We are seeking to conduct 5 focus groups with 7 people each. Phase 2: We are seeking to assess 128 African American adults (64 male; 64 female).

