# [Eligibility Screening Script and Focus Group Script are attached in SmartForms]

Phase 2 – Survey Data: Demographics will include age, biological sex, education, and income. Based upon the behavioral outcomes we expect participants to adopt from the HIV prevention podcasts, we will inquire (pre, 1 mo post, & 3mo): (1) frequency of penetrative sexual intercourse acts in the past month, (2) unprotected penetrative sexual intercourse in the past month, (3) number of sexual partners in

the past month, (4) PhenXToolkit Self-reported HIV Results, and (5) condom use during the last act of penetrative sexual intercourse. Based on the knowledge and psychosocial cognitions we expect to influence, measures (pre & post) will consist of (1) Motivations to use condoms scale, (2) HIV knowledge, (3) attitudes toward condom use, (4) condom use self-efficacy, and (5) condom use communication, (6) perceived social and subjective norms, (7) feedback concerning HIV prevention video content and presentation (1 mo post only), and (8) Marlowe-Crowne social desirability scale(1 mo post only). [A copy of the survey measures is attached in the SmartForm section]

10.4 1 month and 3 month follow-up data will be collected from Phase 2 participants. No follow-up data will be collected form Phase 1 participants.

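### The behaviour items labelled '1 mo post' cover the time before the video, no contrast is named, and there is no comparator; relabel those items, name the contrasts, and restate Aim 2 as within-person change.

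*Combined protocol and SAP*

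**What the plan says.** Aim 2 (section 1.0) is "To evaluate the effectiveness of the two theory-based, video podcast-delivered, HIV prevention interventions for self-identified heterosexual African American males and females". Section 5.3 gives the sample: "We are seeking to assess 128 African American adults (64 male; 64 female"). Section 10.1 describes the design: "Phase 2: The study design is quantitative repeated measures methodology". No control group, waiting list or random allocation appears anywhere.

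Visit 1 is consent and pre-test only (section 8.0). Section 10.2 then has participants receive, one month after pre-test, a link to the "post-test survey in which they will view the podcast video and complete the post-test measures". Section 8.0 describes the same occasion: "The second study visit will consist of a 1 month-follow-up survey video podcast viewing". Its list of durations includes "20 minutes to watch draft podcast video; 15 minutes to complete the posttest". The third survey comes 3 months after the post-test.

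Section 10.3 introduces the behaviour items: "Based upon the behavioral outcomes we expect participants to adopt from the HIV prevention podcasts, we will inquire (pre, 1 mo post, & 3mo"). They are acts, unprotected acts and partners, each over the past month, together with self-reported HIV results and condom use at the last act. The knowledge and psychosocial scales are taken at pre-test and post-test only.

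On analysis, section 9.1 says "The primary study endpoint for the proposed study shall be 3 months following the last" participant's Phase 2 post-test. Section 25.1 plans repeated measures t-tests on the variables of interest, without naming variables or time points.

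**The concern.** The label in section 10.3 invites a reader to treat visit-2 behaviour as an outcome one month after the podcast. By the plan's own schedule it is behaviour one month after pre-test, reported on the occasion when the video is first shown. An analyst who follows the label could compare pre-test with visit 2 and report a one-month behaviour effect that the schedule rules out.

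Separately, Aim 2 promises a conclusion about effectiveness from a design that observes only change within people. Repeated questioning, events in the community and shifts in self-report can all move answers between surveys. A paired test cannot separate these from the podcast at any time point.

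**Working it through.** **The plan's own figures.** 64 + 64 = 128 agrees with the stated total, and 5 + 15 + 20 + 15 + 5 = 60 minutes agrees with section 8.0. No alpha, sidedness, power, effect size, SD or dropout is given, so 128 cannot be re-derived.

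**Step 1: recall windows against the video date.** The schedule comes from sections 8.0 and 10.2, the recall period from section 10.3. Visit 2 is taken as one sitting.

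| Months from pre-test | Occasion | Past-month window | Post-video time in window |
|---|---|---|---|
| 0 | Pre-test | -1 to 0 | none |
| 1 | Visit 2, video first seen | 0 to 1 | none |
| 1 + 3 = 4 | 3-month survey | 3 to 4 | all of it (third month after the video) |

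Last-act condom use and self-reported HIV results have no stated window in the protocol, but at visit 2 they too refer to events before a video seen in the same survey. Of the three possible pairwise behaviour contrasts, pre-test to visit 2 contains no post-video behaviour. The other two both use the 3-month survey. This step needs no assumed effect size.

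**Step 2: does the plan exclude the empty contrast?** Section 9.1 gives a calendar point, not a variable or a contrast. Section 25.1 names a type of test only. Neither excludes it.

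**Step 3: size of the comparator problem.** Assume two-sided alpha 0.05, complete data, no podcast effect, and a drift of d standard deviations of the within-person change. The paired t statistic is then noncentral t with n - 1 degrees of freedom and noncentrality d√n.

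- n=128, √128 = 11.314: d = 0.1, 0.2, 0.3 gives noncentrality 1.131, 2.263, 3.394. The probability of p<0.05 is 0.202, 0.612, 0.920.
- n=64 (for example one sex), √64 = 8: noncentrality is 0.8, 1.6, 2.4. The probability is 0.124, 0.351, 0.657.

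**Step 4: which pre-video baseline?** Let Y1, Y2 and Y3 be pre-test, visit 2 and 3 months, with unit variance.

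- Equal correlation r: Var(Y3 - Y2) = 2(1 - r), and Var(Y3 - mean of Y1 and Y2) = 1.5(1 - r). The mean is more precise.
- Correlation decaying with time at ρ per month, occasions at months 0, 1 and 4: the variances are 2(1 - ρ³) and 1 + (1 + ρ)/2 - ρ³ - ρ⁴.
  - ρ = 0.7: 2(1 - 0.343) = 1.314 against 1 + 0.85 - 0.343 - 0.240 = 1.267.
  - ρ = 0.9: 2(1 - 0.729) = 0.542 against 1 + 0.95 - 0.729 - 0.656 = 0.565.

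Neither baseline is always the more precise. The choice depends on a correlation pattern that the documents do not give.

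**The case against.** The sponsor can answer that the design is openly within-person and never claims randomisation. The endpoint is placed at 3 months, and section 10.2 calls the third survey the behavioural outcome questionnaire. The 1-month wording in sections 8.0 and 10.4 can simply mean one month after pre-test. All of this is fair. The clear mislabel is the one in section 10.3, and placing the endpoint at 3 months does not say which outcome or contrast will be tested.

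Four stronger readings are tempting, and the documents do not support them:

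- **That the plan will report a one-month behaviour effect.** It does not say so. It only leaves that test open.
- **That all of visit 2 is pre-video.** Section 10.2 puts viewing before the measures, and feedback on the video is collected there. Visit 2 is therefore the only post-video value for knowledge, motivation, attitudes, self-efficacy, communication and norms.
- **That power will be lost by pooling visit 2 with 3 months.** No pooling is proposed, so no such loss can be charged to the plan.
- **That the order within visit 2 is contradictory.** Section 10.2 and the list of durations both put the video first. The sentence in section 8.0 that runs survey and viewing together gives no clear order. The survey itself is attached elsewhere and was not available.

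**Conclusion.** The concern holds for the behaviour items and for the wording of Aim 2. The timing conclusion rests on the schedule and on one condition, that visit 2 is completed in one sitting, which the single link in section 10.2 supports. Under that condition, pre-test to visit-2 behaviour change contains no post-video time, and the plan does not keep it out of an effectiveness test.

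The comparator conclusion rests on the design as described: the men and women are the audiences for the interventions, and neither group is set up as a control for the other. The probabilities of 20%, 61% and 92% at n=128 illustrate assumed drifts; the documents give no basis for choosing among them. They show how readily a paired test can be significant with no podcast effect, not that drift will occur.

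**What to change.** 1. For the behaviour items only, relabel visit 2 in section 10.3 as a second pre-video measurement and align section 10.4. In section 25.1, name the behaviour contrast as 3 months versus a pre-video value, either visit 2 or the mean of pre-test and visit 2, chosen in advance. Do not test pre-test to visit-2 behaviour change as a podcast effect. It may be reported descriptively as the change over the untreated month.
2. State the order within visit 2, with the behaviour items asked before the video. If some answers have already been given after the video, use pre-test as the baseline for those, or show both.
3. Keep the psychosocial measures as change from pre-test to immediately after the video, and note that this change includes one untreated month.
4. Restate Aim 2 and its conclusions as uncontrolled within-person change.

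This takes an amendment to wording, analysis text and item order, with no extra participants, visits, questions or payments. The downsides are a weaker claim and possible priming from asking about behaviour just before the video. The changes correct the timing and the claim; they do not supply the missing comparator.

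### Aim 2 evaluates two podcasts, but the protocol text plans no result for each and does not say who views which; behaviour reported at the 1-month post-test also predates viewing

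*Combined protocol and SAP*

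**What the plan says.** - **Aim.** Section 1.0 gives Aim 2 as: "To evaluate the effectiveness of the two theory-based, video podcast-delivered, HIV prevention interventions for self-identified heterosexual African American males and females".
- **Sample.** Section 5.3: "We are seeking to assess 128 African American adults (64 male; 64 female".
- **Analysis.** Section 10.1: "Participant data will be de-identified and used aggregately in repeated measures analyses (N=128". Section 25.1 lists aggregation, removal of identifiers and repeated measures t-tests on the variables of interest. Neither section names podcast, sex, a subgroup or an interaction.
- **Exposure.** Section 10.2 has participants sent a link to "the post-test survey in which they will view the podcast video and complete the post-test measures". The video is singular and no allocation rule is given. Section 8.0 itemises "20 minutes to watch draft podcast video" within a total where "participation in the study is estimated to be about 60 minutes".
- **Measures.** Section 10.3, on behaviour: "we will inquire (pre, 1 mo post, & 3mo): (1) frequency of penetrative sexual intercourse acts in the past month", followed by four further behavioural items. Six psychosocial scales are taken at pre-test and post-test only. Biological sex is a survey demographic with no stated use in the analysis.
- **Endpoint.** Section 9.1 begins: "The primary study endpoint for the proposed study shall be 3 months following the last". It gives a time, not an outcome or a contrast, so it does not settle what is compared.

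**The concern.** There are two gaps, and both bear on whether the planned tests answer Aim 2.

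First, the aim concerns two interventions, while the described analysis has no term that separates them. If all 128 participants go into one paired test, the result is the average of two podcasts' changes. It can be significant when only one podcast is associated with change, and it can conceal opposite changes. If the podcast viewed is neither recorded nor deducible from sex, separate results could not be recovered later.

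Second, the behavioural items are asked at three times, but the middle one is the survey in which the video is first seen. A pre-test to post-test t-test on those items compares two periods that both precede exposure. Its result, in either direction, says nothing about the podcast.

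**Working it through.** **1. How many videos per participant?** The items in section 8.0 are 5 (enrolment), 15 (pre-test), 20 (video), 15 (post-test) and 5 (3-month survey). 5 + 15 + 20 + 15 + 5 = 60 minutes, the stated total. The budget leaves room for one 20-minute video each, but the times are approximate and no sentence says so outright.

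**2. Does the sample size reveal the intended analysis?** The documents give no alpha, power, effect size, SD or dropout, so 128 cannot be reproduced from stated inputs. Assuming two-sided 5% and 80% power:
- Pooled paired t-test, standardised change 0.25: n = 127.5, so 128.
- Two independent means, difference 0.5 SD: 63.8 per group, so 64 per group and 128 in all.

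Both fit. The number does not favour either reading.

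**3. What a pooled estimate can and cannot show.** Assume 64 participants per podcast and unit SD of change within each. With true changes a and b, the pooled standardised change is [(a + b)/2] / √(1 + ((a − b)/2)²).

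| True changes (SD) | Pooled standardised change | Pooled test significant | First podcast's own test significant |
|---|---|---|---|
| 0.25 and 0.25 | 0.25/√1 = 0.250 | 80% | 50% |
| 0.35 and 0.15 | 0.25/√1.01 = 0.249 | about 80% | 79% |
| 0.50 and 0 | 0.25/√1.0625 = 0.243 | 78% | 98% |
| +0.35 and −0.35 | 0 | about 4% | 79% |

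The first three rows look nearly the same when pooled, although the podcasts behave quite differently. The issue is what is being estimated. Power moves in either direction depending on the assumed changes.

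**4. Precision lost by reporting each podcast.** The detectable change at 80% power is roughly (1.960 + 0.842)/√n:
- n = 128: 2.802/11.314 = 0.248; exact t-based value 0.250.
- n = 64: 2.802/8 = 0.350; exact t-based value 0.356.

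The 95% CI half-width, t/√n, is 0.175 SD (n = 128) and 0.250 SD (n = 64). With an assumed 20% dropout (102 and 51), the detectable changes are 0.28 and 0.40 SD.

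**5. Timing of the behavioural items.** Take pre-test as month 0.

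| Survey | Month | Past-month window | Position relative to viewing |
|---|---|---|---|
| Pre-test | 0 | −1 to 0 | before |
| Post-test (video viewed here) | 1 | 0 to 1 | before |
| 3-month follow-up | 4 | 3 to 4 | after |

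Three of the five items carry a past-month window. The other two, condom use at last act and self-reported HIV results, are answered in the same survey as the viewing, so they too report what happened before it. Only the 3-month survey can reflect behaviour after viewing. The six psychosocial scales differ: they can move on viewing, so pre-test to post-test is meaningful for them.

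**6. Number of contrasts.** Six scales with one contrast and five behavioural items with three possible contrasts give 6×1 + 5×3 = 21 paired contrasts. None is specified by podcast.

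**The case against.** The strongest reply is that pooling is not established. In section 10.1 the word *aggregately* is joined to de-identification. In section 25.1 aggregation sits beside the removal of identifiers, and the same word describes the Phase 1 transcripts. It may be confidentiality wording, and N=128 may only restate accrual. That stands: a reader might infer that the plan commits to a pooled test, and the text does not go that far. What remains is that no estimate by podcast is planned on either reading.

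The aim's mention of males and females and the 64/64 accrual suggest one podcast per sex. If so, sex is already collected and the gap is a missing sentence. This is plausible, but no section says it, and sex is not among the screening items listed in section 10.3.

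The SmartForm attachments (screening questionnaire, survey measures, cover letter) were not available, and each participant receives a unique link. A rule could sit there, so the claim is confined to the protocol text.

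The power scenarios can also be chosen to favour either side. With equal changes of 0.25 SD, pooling does better (80% against 50%); with 0.35 and 0.15 SD it matches the stronger podcast's own test. The documents give no reason to expect a podcast to do harm. That stands too, and ranking per-podcast results above the pooled one is partly a preference.

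None of these replies touches the timing of the behavioural items.

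**Conclusion.** The point holds in this form: the protocol text states neither who views which podcast nor any estimate for each, and the pre-test to post-test comparison of the five behavioural outcomes cannot show a podcast effect. The first part is an omission that can be checked in sections 1.0, 8.0, 10.1, 10.2, 10.3 and 25.1. The second follows from sections 8.0, 10.2 and 10.3, given that viewing and measures belong to one survey, as described.

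A reader might infer that the study is unable to answer Aim 2, or that the tabulated power figures measure an error in the plan. The documents support neither. The data needed are largely collected already, and the figures rest on assumed inputs (two-sided 5%, unit SD, 64 per podcast, one podcast per participant, no dropout). They illustrate what an average can hide. This should be fixed before analysis.

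**What to change.** - **Section 10.2.** State which podcast each participant views and by what rule, and record it.
- **Sections 10.1 and 25.1.** Report change with a 95% CI for each podcast (by sex, about 64 each, if podcast follows sex), alongside the pooled N=128 estimate. If every participant views both, say that separate effects cannot be estimated and word the conclusion for the pair.
- **Contrasts.** Use pre-test to post-test for the six psychosocial scales and pre-test to 3-month follow-up for the five behavioural outcomes. Treat the 1-month behavioural values as a second pre-viewing measurement.
- **Limits to state.** All changes are uncontrolled. If podcast follows sex, a difference between podcasts cannot be separated from a difference between the sexes.

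The cost is wording plus one recorded variable. Sex and 3-month behaviour are already collected, and recruitment and surveys are unchanged. The downside is lower precision per podcast (detectable change about 0.36 against 0.25 SD under the stated assumptions) and more tests: 11 outcomes × 2 podcasts = 22 estimates, plus 11 pooled. An adjustment across the two podcasts is optional and would not cover the 11 outcomes.

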### 21.0 Informed Consent Process

- 21.1 The researcher will be obtaining consent:
  - Phase 1: Consent will take place in a closed-door conference room at Jacob's Group Home conference room on the day of anticipated study participation. Phase 2: Consent will take place via the "accept" button on the electronic survey (See Section 22.1).
  - There is no waiting period between informing the prospective subject and obtaining the consent.
  - Phase 1: There will be no ongoing consent. Participation is cross-sectional, meaning no other participation is required upon completion of their focus group. Additionally, participants who were a part of a previous focus group will not be allowed to attend or participate in a subsequent focus group.

Phase 2: There will be no ongoing consent. Consent to the initial pretest (in the form of electronic cover letter – See Section 22.1) will consent participants for the current data collection and follow-ups. Participants are able to leave any question blank they do not wish to answer, or withdraw from the study any time, via email, and no further contact will be initiated (-as stated in the Cover Letter consent information document).

• I will be following "SOP: Informed Consent Process for Research (HRP-090)."

Non-English Speaking Subjects: N/A

Waiver or Alteration of Consent Process (consent will not be obtained, required information will not be disclosed, or the research involves deception):  $N\!/\!A$ 

Subjects who are not yet adults (infants, children, teenagers): N/A

**Cognitively Impaired Adults:** N/A **Adults Unable to Consent:** N/A

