## 25.0 Data Management

- 25.1 Phase 1: Data Analysis will include transcribing the focus group data, examining all the transcriptions aggregately and analyzing the qualitative data for common themes, as thematic analysis will constitute the analysis procedure.
  - Phase 2: Data analysis will include aggregating the data, eliminating any identifiers, and performing repeated measures t-tests on the study variables of interest.
- 25.2 Phase 1: Electronic data (audio files and transcripts) will be secured and encrypted on my on-campus university computer in my office. Consent forms, will be stored in separate folders in a locked file cabinet.
  - Phase 2: Electronic data will be secured and encrypted on my on-campus university computer in my office. Study key code spreadsheet (linking participant ID number with email address) will be encrypted and stored securely on my office computer.
- 25.3 Data will be stored for seven years
- 25.4 Only the PI (researcher) and approved student research team members will have access to the raw data.
- 25.5 The PI (researcher) will be responsible for receipt of the data (Both Phases).
- 25.6 Phase 1: One approved student research team member will have access to the audio files and will be responsible for all audio transcription.Transcription will take place only on the PI's university-issued laptop within the researchers' office during student researcher's work hours. Audio transcription files will be password protected on the UH secure server.

Phase 2: Approved student researchers will have access to the de-identified data. All data analyses will take place only on the PI's university-issued laptop within the researchers' office during student researcher work hours.

25.7 Data will not be banked for future use.

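### The stated repeated-measures analysis size of 128 equals accrual, so with paired t-tests it holds only if nobody drops out and nobody leaves the tested item blank

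*Combined protocol and SAP*

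**What the plan says.** Section 5.1 sets the accrual: "Phase 2: Total number of subjects to be accrued locally = 128". Section 5.3 splits it by sex: "We are seeking to assess 128 African American adults (64 male; 64 female"). Section 10.1 then says the data will be "used aggregately in repeated measures analyses (N=128").

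On waves, section 8.0 says "The number of study visits is 3 per participant", and that the visits "are in the form of online survey and video viewing". Sections 8.0 and 10.2 place them at pre-test, 1 month after pre-test, and 3 months after post-test. Section 10.3 collects the behavioural items at all three waves, but the knowledge and psychosocial scales only at pre-test and post-test.

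The analysis in section 25.1 is "performing repeated measures t-tests on the study variables of interest". Sections 13.2, 16.2 and 20.0 let participants stop at any time. Section 21.1 adds: "Participants are able to leave any question blank they do not wish to answer". The documents give no dropout allowance, replacement rule or missing-data method, and no sample-size justification.

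**The concern.** A paired t-test uses only people who have both values of the pair. When enrolment and analysis size are the same number, any lost participant or blank item makes the analysis smaller than the plan says.

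The pre-to-3-month comparison carries the most risk because it accumulates loss over both later waves. It also matters most for behaviour. The podcast is viewed inside the post-test survey (section 10.2), so past-month items answered there describe the month before viewing. Section 9.1 also places the study endpoint 3 months after the last post-test.

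Two things are at stake. A reader of section 10.1 is given an analysis size that the design is unlikely to deliver. In addition, the people left after pairwise deletion may differ from those enrolled. Section 13.2 itself expects some participants to find the sexual-behaviour questions uncomfortable and encourages those in significant discomfort to leave. If loss depends on risk behaviour, the change among complete pairs is not the change in the enrolled group.

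**Working it through.** **The plan's own figure.** No derivation is given, so 128 cannot be reproduced from stated inputs. At an assumed two-sided 5% and 80% power, two designs fit it: a two-group comparison at 0.5 SD (63.8, so 64 per group, 128 in all) and a paired t-test at 0.25 SD (127.5, so 128 pairs). The documents state neither.

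**Pairs available.** With a proportion *d* lost by the compared wave, pairs = 128 × (1 − *d*), which equals 128 only at *d* = 0. A blank on the tested item removes a pair in the same way, so *d* has to cover both. By sex, the formula is 64 × (1 − *d*).

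**Detectable change.** This is the standardised paired change with 80% power, from the noncentral *t* distribution with *n* − 1 degrees of freedom, two-sided 5%. The loss rates, alpha and power are assumptions.

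| Loss | Pairs, all | Detectable change (SD) | Power at 0.25 SD | Pairs, per sex | Detectable change (SD) |
|---|---|---|---|---|---|
| 0% | 128 | 0.250 | 80% | 64 | 0.356 |
| 10% | 115 | 0.263 | 76% | 58 | 0.374 |
| 20% | 102 | 0.280 | 71% | 51 | 0.400 |
| 30% | 90 | 0.299 | 65% | 45 | 0.427 |
| 40% | 77 | 0.323 | 58% | 38 | 0.467 |

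Pairs are rounded to the nearest whole number. If loss were 10% at each of the two later waves, pre-to-post would keep 128 × 0.9 = 115 and pre-to-3-month 128 × 0.9² = 104. The two comparisons therefore need separate expected numbers.

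**Bias from deletion.** Take an outcome with no true change, unit SD and an assumed correlation ρ between waves. Let 40% of those above the baseline median drop out, and 10% of the rest (assumed). The mean of a standard normal above its median is 0.798, so the retained baseline mean is (0.6 × 0.798 − 0.9 × 0.798) / 1.5 = −0.16, and the retained follow-up mean is −0.16ρ.

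- Complete pairs: change = −0.16ρ + 0.16 = 0.16(1 − ρ). At ρ = 0.5 this is +0.08 SD.
- Unweighted GEE with independence working correlation, which compares the retained follow-up mean with the full baseline mean: −0.16ρ. At ρ = 0.5 this is −0.08 SD.
- Likelihood-based model using all baselines: about 0.

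For ρ from 0.3 to 0.7, complete-pair bias runs from +0.11 to +0.05 SD and independence-GEE bias from −0.05 to −0.11 SD. A simulation gave the same values.

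**The case against.** The strongest reply is that the 128 in section 10.1 merely repeats the enrolment target in a one-sentence design description and promises nothing about complete pairs. That reading is possible, and if it is the intended one, the sentence should say so.

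A reader might go further and infer that the trial is underpowered or that its precision is overstated. The documents do not support this. They state no alpha, power, effect size, SD or interval width, so there is no claim to fall short of. The 0.25 SD reference is back-solved from 128. The loss rates are assumptions too, and at 20% loss the detectable change moves only from 0.25 to 0.28 SD.

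A reader might also take 64 as the planned number per podcast. Section 5.3 gives 64 men and 64 women. Section 1.1 names two interventions, but no section assigns a podcast by sex or gives a number per podcast.

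Three further points stand. The SD-unit figures suit continuous scales, whereas several items in the 3-month survey are counts or binary. The knowledge and psychosocial scales need retention only to the 1-month wave. The plan also has features that may help retention: payments of $20, $80 and $25, and completion at a community center if needed. These may reduce loss, but they are not a dropout allowance. Payment requires a submitted survey, not a fully answered one.

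**Conclusion.** The point holds as a mismatch between the stated analysis size, the accrual and the method. With 128 enrolled and paired t-tests, 128 analysed requires zero dropout and no blank on the tested item. That follows from the text alone and needs no assumption.

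Its size does rest on assumptions. Under 10% to 40% loss, between 115 and 77 pairs remain, and the detectable change on a continuous scale rises from 0.25 SD to between 0.26 and 0.32 SD. The exposure is greatest for pre-to-3-month behaviour. Bias is a separate issue: it arises only if loss is related to the outcome, and the 0.08 SD example shows what could happen, not what is expected.

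This does not establish a failure of power, and it does not require more participants. The plan should be corrected on both counts, the stated number and the handling of incomplete data, because neither correction needs new data.

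**What to change.** Keep accrual at 128.

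1. In section 10.1, label 128 as the number enrolled. State the expected analysable pairs for pre-to-post and for pre-to-3-month, overall and by sex (64 men and 64 women enrolled), under a stated retention assumption for each wave that also allows for blank items.
2. In section 25.1, replace the complete-pair t-tests with a likelihood-based repeated-measures mixed model, using every completed wave from everyone with a pre-test. Use a generalised linear mixed model for count and binary items. GEE is acceptable only with inverse-probability weighting or multiple imputation; unweighted independence GEE should not be used.
3. State that the analysis relies on data being missing at random and does not correct dropout that depends on unobserved later behaviour.

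The cost is protocol wording, slightly more analysis work and a less favourable stated analysis size. Participants with only a pre-test add little direct information on change, so the model will not restore the precision of 128 complete pairs.
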